The real-world distribution of race and ethnicity of patients varies across practices as a function of the residents of neighborhoods from which the practices draw. Although we continue to attempt to recruit up to 21 non-Hispanic white, non-Hispanic African-American, and Hispanic eligible patients at each practice, we acknowledge this variation and are aware that in some practices we will not be able to meet the recruitment goals for each race or ethnicity. In order to approach a somewhat balanced distribution in the overall analytic sample, we will oversample non-Hispanic African Americans in practices with high percentages of African-American patients and Hispanic patients in practices with high percentages of Hispanic patients. In turn, there are practices with percentages of whites so low that we are unlikely

to reach 21 participants. We have already de facto oversampled non-Hispanic whites in several practices because of low numbers of eligible participants in the other two targeted racial and ethnic groups.

We do not know the exact racial and ethnic distribution of patients eligible for our study until we receive recruitment data for each practice. Thus, to date, we have not able to predetermine a race/ethnicity oversampling plan. As additional practices join the study, however, we will over-recruit among Hispanics to increase balance among the three groups at the overall sample level. This will require that we recruit additional Hispanic hypertensive patients at the remaining 20 practices. It should be noted that these additional patients will be recruited in lieu of white patients in order to keep the average number of patients at CC/Stepped care practices at close to 63 (for care management purposes). It is our goal to obtain a sample of sufficient size to analyze Hispanics separately; however, the group size may ultimately be limited to 10% of the overall sample.

With respect to balance across intervention arms, we may face greater challenges reaching goals for Hispanic patients due to allocation of practices through randomization.

[figure not shown]
E. Participant Screening and Consent:

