For the important clinical outcome of BP control we will model the binary variable BP controlled (yes/no) at 12 and 24 months together using GEE with a logit link, and with the intervention arm indicator (CC/Stepped Care arm vs. SCP arm), the follow-up visit indicator (24 months vs. 12 months), and the interaction term of these two binary indicators as the main predictors for the mean model. Additional covariates will be included as appropriate as described previously. Multiple imputation of missing BP outcomes will be carried out to impute the missing BP control outcomes to produce proper inferences under MAR and to conduct sensitive analyses under NMAR scenarios.

For the durability outcomes of change in blood pressure and Patient Activation at 24 months, we will derive the statistical inference from mixed-effects models utilizing all outcome measures available from the 3 study time points. The regression coefficients of the arm by 24-month visit cross-product interaction term from the corresponding models estimate the difference in change in systolic BP as well as the difference in change in PAM-13 at 24 months from baseline between the intervention and the control arm, respectively. Estimates contrasting the 24 months change to the 12 months change from the modeling results will allow us to assess the durability or late effect of the intervention.

Subgroup Analyses

Patients, clinics, and health systems will be keen to know if the interventions have differential effects on different subpopulations. The pre-specified subgroup analyses include analyses by race and ethnicity. Specifically, we will compare outcomes among non-Hispanic African Americans and Hispanics to non-Hispanic whites. The analysis plan for testing heterogeneity of treatment effects is that using the full dataset, we will compare each disadvantaged subgroup (and the combined disadvantaged groups) to the presumed-advantaged group. We will test interactions of these with the intervention effect. We targeted enrolling approximately 21 patients in each race/ethnicity category per clinic to maximize power; however, these analyses will be exploratory and are not powered to detect specific differences among the subgroups.

Exploratory analysis will also be conducted to test for differential intervention effects across clinics. For this analysis clinic-indicator dummy variables and their interaction with intervention arm will be included in the GEE and mixed effects models.

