For the CC/Stepped Care arm, exploratory analysis will be conducted to determine which parts of the intervention, e.g., number of CM and CHW contacts, were more successful in improving BP control and reducing systolic BP, or if there was an overall “dose” effect.

Power calculation

We aim to recruit a total of $n=1,890$ unique patients. We planned for 20% random attrition which would yield an analytic sample of 1,500 (effective size of 50 patients per practice).^{104,105} A review of cluster-randomized trials in primary care found a median intracluster correlation coefficient (ICC) of 0.04, with an interquartile range of -0.02 to 0.21.¹⁶⁴ Assuming a 5% ICC, 15 clusters of 50 patients per intervention arm and a two-sided alpha of 0.05, we will have 80% power to detect a difference in proportion of patients with BP controlled of 11-13% (depending on whether the proportion controlled in the SCP arm is 50%-70%). With the same assumptions and sample size, using a two-sample t-test, we will be able to detect an effect size of 0.278. Operationalizing this for the primary and important secondary outcomes, we anticipate that for PAM-13, estimating a $SD=10.0$,¹⁶⁵ we would be able to detect a mean difference of 2.78 between the CC/Stepped Care and SCP arms; for systolic BP, estimating a $SD=19.5$ mm Hg,¹⁵³ we could detect a mean difference of 5.42 mm Hg between the CC/Stepped Care and SCP arms.

Design Considerations:

Participants will be considered to be enrolled at the time they are given their randomization assignment, which will occur at the end of the baseline interview. Data from all enrolled participants will be analyzed as intent-to-treat.

Missing Data

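### The race/ethnicity-by-arm interaction mixes within-practice and between-practice differences in effect; report the two parts beside the planned pooled test

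*Combined protocol and SAP*

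**What the plan says.** Under Subgroup Analyses, Section 8 specifies that "using the full dataset, we will compare each disadvantaged subgroup (and the combined disadvantaged groups) to the presumed-advantaged group", and then: "We will test interactions of these with the intervention effect". The same paragraph labels these analyses exploratory and unpowered. The models are those of the General Approach: a practice random effect for continuous outcomes, and GEE with exchangeable correlation and robust inference for binary outcomes. Cluster-level characteristics may enter as covariates. Nothing separates same-practice contrasts between groups from contrasts between practices.

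Section 5D describes the sampling. It still aims for up to 21 patients of each group per practice, but expects to miss that at some sites and adds that "we will oversample non-Hispanic African Americans in practices with high percentages of African-American patients and Hispanic patients in practices with high percentages of Hispanic patients". It also says that whites have already been oversampled in several practices, that extra Hispanic patients will take the place of white patients at the remaining practices, and that Hispanics may end up as only 10% of the sample.

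**The concern.** A patient's arm is the arm of the practice. A race-by-arm coefficient from a random-intercept or exchangeable model is a precision-weighted mix of two slopes: the difference in effect between groups inside a practice, and the change in effect from practices with a low share of the group to practices with a high share. Clustering adjustment down-weights the second slope but does not remove it. Practice covariates entered as main effects do not absorb practice differences in treatment effect.

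The separate clinic-by-arm analysis in Section 8 does not help. It is not part of the race model, and because arm is constant within a clinic, clinic dummies and their products with arm are collinear.

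Practice effects could plausibly vary with mix. The sample combines FQHCs with a non-FQHC system, and Sections 3F and 4E leave staffing and spending to each system. Specific Aim 1 is to reduce disparities, and this is the only planned test of whether the effect differs by race or ethnicity. A reader of the pooled coefficient could not tell a patient-level difference from a difference in how the programme worked in certain practices.

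**Working it through.** **The plan's own figure.** Section 8, Power calculation: "Assuming a 5% ICC, 15 clusters of 50 patients per intervention arm and a two-sided alpha of 0.05, we will have 80% power". The design effect is 1 + (50 − 1) × 0.05 = 3.45, so 750 / 3.45 = 217.4 effective patients per arm. With 28 df, (2.048 + 0.855) × √(2 / 217.4) = 0.278, as stated; 0.278 × 19.5 = 5.42 mm Hg, also as stated. This is for the main effect. The documents give no figure for the interaction.

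**Weight on the between-practice slope.** Let p be a group's share in a practice, Vb the variance of p across practices, and Vw the mean of p(1 − p). With m = 50 and ICC ρ = 0.05,

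w = (Vb / 3.45) / (Vb / 3.45 + Vw / 0.95).

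If the within-practice interaction is zero and the effect changes by G as p goes from 0 to 1, the pooled interaction is about w × G. All shares below are assumptions. The simulation used 1,000 runs per scenario, 30 practices × 50 patients, robust SE with t(28), G = 0.6 SD (0.6 × 19.5 = 11.7 mm Hg) and no within-practice interaction.

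| Assumed shares | Vb | Vw | w | Simulated pooled bias | Rejection, pooled |
|---|---|---|---|---|---|
| Same everywhere | 0 | – | 0% | – | – |
| 50-82%, evenly spread | 0.009 | 0.215 | 1% | 0.005 SD | 4% |
| 20-100%, evenly spread | 0.057 | 0.183 | 8% | 0.04 SD | 5% |
| 10 practices each at 10, 66, 96% | 0.127 | 0.118 | 23% | 0.14 SD | 16% |
| 15 each at 6, 96% | 0.2025 | 0.047 | 54% | 0.31 SD | 45% |

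For the fourth row: (0.127 / 3.45) / (0.127 / 3.45 + 0.1176 / 0.95) = 0.0368 / 0.1606 = 0.229, and 0.229 × 0.6 = 0.137 SD. The within-practice term had mean bias within ±0.01 SD and 3-5% rejection in every scenario. Practice variation in effect (SD 0.2) unrelated to mix gave no bias and about 5% rejection.

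**BP control, moderate clustering.** Assume a share of 45% in 4, 6, 10 or 15 practices and 2% elsewhere, with an effect 10 points larger in the high-share practices, so G = 0.10 / 0.43 = 23.3 points. Then w = 10.5, 11.1, 10.6 and 8.7%, giving 2.4, 2.6, 2.5 and 2.0 points. Simulation (700 runs) gave 2.8, 2.0, 2.5 and 2.3 points pooled, and 0.3, −0.5, 0.0 and 0.3 within practice. The SD of the estimate was 10.5, 9.1, 7.8 and 6.3 points pooled, and 10.9, 9.7, 8.2 and 6.6 within: 4-7% larger.

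**Three groups, systolic BP.** Assume the same composition in both arms, no within-practice interaction, and an effect 5.42 mm Hg larger only in Hispanic-heavy practices.

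- Three such practices per arm (white/Black/Hispanic 10/8/32; Hispanics 14% of the sample): the Hispanic-by-arm term shows 2.06 mm Hg.
- Two per arm (3/5/42; 12% of the sample): 3.08 mm Hg.

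Over both mixes and ICCs from 0.02 to 0.20, the range is 4.01 down to 0.68. With the larger effect in African-American-heavy practices instead, that group's term shows 1.46 to 2.16 mm Hg at ICC 0.05. With an even mix all are zero.

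**ICC.** The plan cites a "median intracluster correlation coefficient (ICC) of 0.04, with an interquartile range of -0.02 to 0.21". A higher ICC lowers w: for the 10/66/96% mix it is 35% at ICC 0.02 and 7% at 0.20.

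**Cost in precision.** With no gradient, the SD of the interaction goes from 0.127 to 0.146 (15%) for the 10/66/96% mix and from about 0.16 to 0.23 (about 44%) near separation.

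**The case against.** The strongest reply is that the distortion is small where clustering is moderate. In the BP-control scenario a 10-point practice difference, close to the trial's whole detectable effect of 11-13 points, produces a false 2.0-2.8 points, or 0.22-0.37 of the estimate's own SD. Root mean square error is nearly the same either way: for four high-share practices, √(10.5² + 2.8²) = 10.9 pooled, against 10.9 within. This stands. It is why the split should accompany the pooled test and not replace it.

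Second, the clustering is assumed. Section 5D also starts recruitment at each practice with the least represented group and keeps the target of 21 per group. Both work against concentration, though the section concedes shortfalls of unknown size.

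Third, a reader might infer that only the within-practice difference bears on disparities. The documents do not say so. Section 8 asks about different subpopulations without restricting the comparison to patients of one practice, and the Background counts practice settings and local community among the barriers. Preferring one component is a choice of estimand.

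Finally, the analysis is declared exploratory and unpowered. That lowers the stakes but does not settle what the coefficient means.

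**Conclusion.** The planned interaction is a blend, and the plan offers no way to take it apart. If the intervention effect tracks racial mix, about 1-10% of the gradient from 0% to 100% share enters the pooled term under mild to moderate clustering of groups, and about 20-55% under strong clustering, at ICC 0.05 and 50 patients per practice. The Hispanic contrast is the most exposed, because that group may be small and held in few practices.

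A reader might go further and conclude that practice differences in effect will be reported as race differences. The documents do not support that. They give neither the mix by practice nor any sign that effects follow it, variation unrelated to mix does no harm, and transfer is partial even when the condition is met. Rejection rates of 16-45% arise only with strong or near-complete separation and a steep gradient (11.7 mm Hg across the full range of shares). The primary analyses are untouched. This is a minor, inexpensive improvement to an exploratory analysis.

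**What to change.** Keep the planned pooled interaction. Alongside it, replace each group indicator by the practice proportion of that group and the patient's deviation from that proportion, and cross both with arm. Report the within-practice and practice-composition interactions together. Read a pooled interaction as patient-level only if the within-practice term agrees with it. Tabulate race/ethnicity by practice and arm, including how many practices per arm contain both groups of each contrast, so that readers can see which clustering scenario applies.

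No new data are needed. With two minority contrasts the model gains two share terms and two share-by-arm terms on 30 practices. The within-practice standard error is about 5% larger than the pooled one under moderate clustering, about 15-25% under strong clustering, and up to about 44% near separation. Composition terms may rest on very few practices, especially for Hispanic patients, and should be described as such.

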1. **UH3 Specific Aim 1:** We will conduct a pragmatic clinical trial to test practical, scalable approaches to close the HTN disparities gap. We will compare the effectiveness of a standard of care plus (SCP) intervention (that includes audit/feedback and education) to practice-based collaborative care with a stepped approach (CC/stepped care) that includes community-based contextualized care delivered by a CHW, specialist consultation, or both, to reduce disparities in HTN and improve patient-centered outcomes (self-management behaviors, goal attainment, activation).
2. **UH3 Specific Aim 2:** We will demonstrate patient and stakeholder engagement by applying principles of community-based participatory research (CBPR) to build upon our existing local community board and engage a regional and national stakeholder advisory panel.
3. **UH3 Specific Aim 3:** This study will inform the important question of whether a multi-level intervention that adds a contextualized (i.e., patient and family-centered, community-based) approach to practice-based CC/stepped care will be more effective than SCP alone at improving clinical outcomes and self-management behaviors among patients with hypertension and other common comorbidities and CVD risk factors.

- i. UH3 Hypothesis:** The multi-level intervention with a contextualized (i.e., patient and family-centered, community-based) approach to practice-based CC/Stepped Care will be more effective than SCP in improving clinical outcomes and self-management behaviors among hypertensive patients with other designated conditions.

A. Research design/methodology

1. The design of this study is a prospective cluster-randomized trial of superiority of CC/Stepped Care over SCP. Evidence exists for the effectiveness of both intervention approaches; however, they have not been sustained or translated to practice in real-world settings caring for underserved populations. Further, the proposed comparison has not been done, using a pragmatic approach, to address HTN management to reduce disparities in patient outcomes (see Section 1: Background/Significance).

B. Study population: Inclusion/exclusion criteria

1. Inclusion Criteria:

- a. Practice sites: Thirty primary care clinics in the mid-Atlantic have been enrolled and randomized. Practices must either be Federally Qualified Health Centers (FQHCs) or serve diverse racial and ethnic populations.

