The randomization of replacement practices is described on pages 21 and 22.

2. **Phased intervention rollout.** Different health systems began the intervention on a staggered basis (see Figure 1: Phased intervention roll-out). Beginning in the UH3 phase, we distributed automated devices to train staff on evidenced-based BP measurement, audited fidelity to the BP measurement protocol, and enrolled patients, which for the first 9 practices took 6 months. Thereafter, the 21 additional practices began the intervention, starting at least 3 months after the first 9 practices. Intervention roll-out will continue until all 30 practices have implemented either SCP or CC/Stepped Care. As practices complete the intervention, we will continue to monitor outcomes data to assess sustainability.

Figure 1: Phased Intervention Roll-out

H. Expected duration of subject participation

The intervention period for the entire study will last three years, but each set of practices will have at least one year of active collaborative care intervention. Discipline-specific clinician and staff training on the interventions will occur in all practices prior to their assigned roll-out date during practice orientation. Each patient participant will be exposed to two years of active intervention.

Section 4: Recruitment of practices

[figure not shown]
There are two levels to our site recruitment strategy. We began by identifying multi-practice systems with which to partner. Generally, the systems agreed to include all of their participating adult medicine sites in the study; however, in one large system, there were more site locations than needed to include to reach the desired power level. Furthermore, we wanted to use the large, non-FQHC private nonprofit system to provide a counterpoint to the included FQHCs without overwhelming them in number.

A. Number of practice sites: Thirty primary care practices across Maryland and Pennsylvania have been enrolled and randomized.

B. Practice inclusion/exclusion criteria:

1. Practices must be FQHCs or other primary care practices that serve diverse racial and ethnic populations
2. Practice demographics: From the FQHCs, we preferentially included larger practices. From the non-FQHC health system (JHCP), we preferentially selected practices with larger populations of ethnic minorities and patients from underserved communities, including sites with a greater likelihood of drawing from rural areas.

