5. **Employment of risk-stratified CC protocols.** The experimental intervention is implemented at half of the practices (n=15). This multilevel intervention includes the practice-based CC team with the option of stepping patients up (if their SBP remains ≥ 140 and/or DBP ≥ 90 after 3 months or 1 month in extenuating circumstances) to either obtain subspecialist consultation or to see a CHW. The CHW is an integrated member of the team and supports patients in reaching their self-management goals; helps patients address social and environmental barriers to engaging in care through outreach and navigation services; and engages, activates, and empowers patients and their support system to participate in the care process. After three additional months (or one month in extenuating circumstances), if a patient's BP continues to be uncontrolled or becomes uncontrolled, the CC team has the option of stepping the patient up again (adding either subspecialist consultation or CHW, as guided by the protocol). Thus patients in CC/Stepped care can receive CC only; CC+CHW; CC+Specialist; or CC+CHW+Specialist care.

The CM may deploy a CHW prior to one month if the patient is willing to work with a CHW AND at least one of the following conditions is met: no-show or difficult to engage patient; cardiac event in the last 12 months, with no follow-up appointment; inability to perform activities of daily living with no resources; no access to transportation; utility shut offs; food insecurity; domestic violence; poor/unstable housing; special request from the patient and/or the PCP.

6. **Reassessment at determined intervals or milestones.** Patients in CC/Stepped Care are reassessed per protocols based on their levels of BP and CVD risk factor control, weekly, biweekly, or monthly, until goals are attained.

B. Intervention approach: In UH2, our intervention was a stakeholder engagement process to plan and test recruitment for the trial. In UH3, we are conducting a two arm, prospective cluster-randomized trial and study of multi-level factors affecting implementation, quality improvement & disparities.

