We will use mixed-effects regression models for continuous outcomes and Generalized Estimating Equations (GEE) analysis for dichotomous outcomes. For mixed-effects regression modeling, we will assume an unstructured correlation structure for longitudinal analyses of outcomes with repeated measurements over time, employ random effects to address clustering by practices, include appropriate covariate adjustment in the fixed effects, and use robust estimates for statistical inferences. The GEE approach is robust to outcome correlation misspecification, so we will just assume an exchangeable correlation structure for the outcomes, include appropriate covariates in the mean model, and use robust estimates for statistical inferences. We will use mixed-effects regression models under the MAR assumption as the basis to conduct multiple imputation for missing BP data or other outcomes as appropriate. In sensitivity analyses evaluating potential impacts under sensible informative missing

(NMAR) scenarios, we will preserve the mixed-effects regression based variance-covariance estimates, and manipulate the mean model under each informative missing scenario to carry out multiple imputation. Missing binary outcomes (e.g., controlled BP or lipids) will be derived based on multiple-imputed continuous values using appropriate observed data likelihood models as described.

Statistical analysis plan for primary outcomes

For the primary clinical outcome of BP control at 12 months we will model the binary variable BP controlled (yes/no) at 12 months using GEE with a logit link on the intervention arm indicator (CC/Stepped Care arm vs. SCP arm). Additional covariates will be included as appropriate as described previously, including appropriate cluster level characteristics and variables associated with occurrence of missing data. With correctly specified mean model, the GEE is robust to misspecification of correlation structure so the statistical inferences will account for outcome correlation due to patients clustering within practice and be valid under MCAR. The regression coefficient for the intervention arm indicator estimates the log-odds ratio of BP control at 12 months for the CC/Stepped Care arm to the SCP arm. Multiple imputation of missing BP outcomes will be carried out to impute the missing BP control outcomes to produce proper inferences under MAR and to conduct sensitive analyses under NMAR scenarios.

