For the primary patient-reported outcome of change from baseline in PAM-13 score at 12 months, we will model the baseline and 12-month PAM-13 measurements using a mixed-effects linear regression model, with the intervention arm indicator (CC/Stepped Care arm vs. SCP arm), 12-month time indicator, and the cross-product term of intervention by time interaction as the fixed mean effects, the practice indicator as a random effect, and additional covariates included as fixed effects as appropriate as described previously. The fixed effect regression coefficient for the cross-product term of intervention by time estimates the mean difference of 12 month change in PAM-13 between arms.

Statistical Analysis Plan for Secondary Outcomes

For the outcomes of systolic and diastolic BP measures at 12 months, we will select the blood pressure measure that is closest to 12 months of follow-up for each patient as long as it is within the 6-month window (either direction). We will model the baseline and 12-month BP measurements using a mixed-effects linear regression model, with the intervention arm indicator (CC/Stepped Care arm vs. SCP arm), 12-month time indicator, and the cross-product term of intervention by time interaction as the fixed mean effects, the practice indicator as a random effect, and adjusting for additional covariates as fixed effects as described previously. The random effect for the cluster ID will be used to capture the outcome correlation for patients nested within the cluster. The fixed effect regression coefficient for the cross-product term of intervention by time estimates the mean difference of 12 month change in BPs between arms.

For the other secondary measures, e.g., laboratory measures of hemoglobin A1c and lipids, we will use methods similar to the assessment of 12 month outcomes for blood pressure, i.e., select the within window measure in the EMR closest to 12 months after baseline and use mixed-effects linear regression or GEE models to assess the outcomes while controlling for outcome clustering within practice.

Subgroup and Exploratory Analyses

Durability of intervention effect at 24 months

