4. *Randomized trial:* The human subjects in this phase of the proposed research are 1,890 patients with hypertension (HTN) and associated comorbidities who receive their primary healthcare at partnering health systems, as well as the clinicians and staff of each practice and leadership of the systems to which the practices belong. The research will include an average of 63 patients at each of the 30 participating practices within these health systems. As our study design is a cluster randomization of practice sites, not participants, patients will be assigned to the study condition, SCP or CC/Stepped Care intervention arm, of the practice they attend for healthcare. Patients are surveyed prior to learning the random assignment of their practice and are given information on each condition and asked if they are willing to participate, given that they may end up in either condition. Clinicians and staff will be asked their opinions about their workplace and their satisfaction with the program. Leaders will be asked about the capacity and priorities of their systems.

b. **Adequacy of Protection Against Risks and Potential Benefits**

- i. **Education in protection of human research participants:** Education in the protection of human research participants and good clinical practice has been met by certified completion of the Johns Hopkins University School of Medicine or School of Public Health Web-based Research Compliance course, “Human Subjects Research Training” by all relevant Key Personnel. The course consists of the University of Minnesota Web modules on Informed Consent, the Consent Process, and After Informed Consent, a Johns Hopkins University School of Medicine module on local IRB requirements, and achievement of a passing score on the Johns Hopkins Knowledge Assessment module. Training in the Health Insurance Portability and Accountability Act (HIPAA) has also been met by certified completion of the Johns Hopkins University School of Medicine’s Web-based HIPAA training course.
- ii. **Recruitment and Informed Consent:**
 1. *Recruitment for Kick-Off/Town Hall Meetings:* Identified stakeholders in the proposed research are invited to attend town hall meetings by letter/email from the Principal Investigators (PIs). Letters are sent at least two months prior to meetings to allow adequate planning time for stakeholders.

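### The planned clinic-by-arm interaction cannot be estimated, because every clinic belongs to one arm only

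*Combined protocol and SAP*

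**What the plan says.** Under Subgroup Analyses in Section 8, an exploratory analysis is meant to test for differential intervention effects across clinics. The method is stated in one sentence: "For this analysis clinic-indicator dummy variables and their interaction with intervention arm will be included in the GEE and mixed effects models".

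The design is fixed elsewhere in the same document:

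- Section 3B, practice sites: "Thirty primary care clinics in the mid-Atlantic have been enrolled and randomized".
- Section 3G, phased rollout: "Intervention roll-out will continue until all 30 practices have implemented either SCP or CC/Stepped Care".
- Section 6A, item 5, gives 15 practices to CC/Stepped Care; Section 6B gives SCP the other half.
- Risks to Human Subjects, randomized trial: "patients will be assigned to the study condition, SCP or CC/Stepped Care intervention arm, of the practice they attend for healthcare".

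The models that would receive the clinic terms are also in Section 8. The primary BP-control model is a logit GEE at 12 months, for which "the statistical inferences will account for outcome correlation due to patients clustering within practice". The General Approach says the GEEs will assume an exchangeable correlation, "include appropriate covariates in the mean model, and use robust estimates for statistical inferences". The mixed models for PAM-13 and blood pressure use arm, time and "the cross-product term of intervention by time interaction as the fixed mean effects", with practice as a random effect. The 24-month durability analysis uses a GEE on the 12- and 24-month BP-control outcomes together, and mixed models on three time points.

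**The concern.** A clinic-by-arm interaction asks how the CC-versus-SCP contrast changes from clinic to clinic. That needs both arms inside a clinic, and here arm is constant within every clinic. The word clinic cannot be read as health system (where both arms can occur): the same subsection names clinics and health systems separately, and its target of about 21 patients per race/ethnicity group per clinic is the per-practice target of Section 5D.

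Two things are at stake. The analysis cannot answer its stated question. And the software will probably not stop: it will drop aliased columns and print the clinic terms that remain, which could then be reported as heterogeneity of treatment effect.

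**Working it through.** **The plan's own figure.** The documents give no figure for this exploratory test. The only calculation on the 30-clinic design is the power statement in Section 8: 15 clusters of 50 per arm, ICC 0.05, two-sided 0.05, 80% power. Design effect = 1 + 49 × 0.05 = 3.45; effective n per arm = 750 / 3.45 = 217.4. A t-test with 30 − 2 = 28 df gives a detectable effect of 0.278, as stated. On the same effective n, the detectable BP-control differences are 13.3, 12.7 and 11.5 points for SCP control of 50%, 60% and 70%, consistent with the stated 11–13%. That calculation is sound; it is used below only to scale one alternative.

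**Algebra.** Let D_c be the dummy for clinic c and A the arm indicator (1 = CC/Stepped Care).

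- A is the sum of D_c over the 15 CC clinics, so it is a linear combination of the dummies.
- A × D_c equals D_c if c is a CC clinic and is zero if c is an SCP clinic.

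Of the 60 clinic-by-arm cells, 30 are empty by design.

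**Rank check.** This needs only 30 clinics, 15 per arm. The mean model is intercept, arm, 29 clinic dummies and 29 products, plus time and arm-by-time terms where the model has them.

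| Model | Columns | Rank | Clinic-by-arm terms estimable | Common arm term |
|---|---|---|---|---|
| Single-time GEE | 60 | 30 | 0 of 29 | arm effect not estimable |
| Two times (baseline/12-month mixed model; 12/24-month GEE) | 62 | 32 | 0 of 29 | arm-by-time estimable |
| Three-time mixed model | 64 | 34 | 0 of 29 | arm-by-time estimable |

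The plan does not write clinic-by-arm-by-time terms. They are the obvious attempted rescue, since the longitudinal effect is a difference in change, so they were checked too. With every clinic term crossed with time there are 120 columns of rank 60 (two times) or 180 of rank 90 (three times). None of the 29 clinic-specific terms is estimable at any follow-up, and the common arm-by-time term is lost as well. Repeated measurement gives each clinic its own change, but still no comparator.

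**What the output would look like.** Logit GEEs were simulated with practice as cluster, aliased columns removed and no true clinic differences. Assumptions: 30 × 50 patients, 60% controlled, one standard-normal patient covariate with log-OR 0.3, ICC 0.

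- Single time, working independence: median robust SE of the kept clinic terms 0.007, against a model-based 0.41 and an empirical SD of 0.42; 97% had |z| > 1.96. With ten covariates: 0.038 and 88%. With no covariates: below 2e-15.
- Single time, exchangeable as planned: 0.007 and 97%. The dummies force the working correlation to about −1/49 = −0.02, so the model-based SE (0.06) is also too small.
- 12/24-month, working independence, adding a patient random-intercept variance of 3.3: 0.005 against an empirical SD of 0.34; 97%.
- With ICC 0.05, single time, one covariate: 0.008 against 0.42.

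The cause is structural. Each kept dummy fits its own cluster's total almost exactly, so the cluster-level residual sums that feed the sandwich estimator are close to zero.

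**The case against.** The strongest reply is that little turns on this. The analysis is labelled exploratory, the main analyses contain no clinic fixed effects, and dropped columns would alert the analyst. That is a fair limit on its importance, and it stands. It does not make the analysis estimable, and dropped columns are no safeguard when the remaining terms look highly significant.

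The false-significance result is conditional. The plan does not name the cluster unit for the 12/24-month GEE; practice is inferred from the primary-outcome text. With patients as clusters, a small run (8 replicates) gave a robust SE of 0.34 and only about 1–3% of terms beyond 1.96. Even with practice clusters the size depends on which columns are dropped: under another choice the CC clinic terms had an SE of 0.06 with 85% beyond 1.96, still understated about 5- to 6-fold. Rank alone proves the main point; the simulations describe a hazard.

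A random clinic effect in place of the dummies might be proposed. The sentence puts the terms in the mean model. A random arm effect by clinic is in any case confounded with between-clinic variance in the CC arm unless that variance is assumed equal across arms without the intervention.

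**Conclusion.** The concern holds. As written, the test cannot estimate or test any clinic-specific intervention effect in any of the planned models: 0 of 29 interaction terms are estimable. In the single-time GEE the clinic dummies also remove the arm effect. This rests only on the cluster allocation in the documents, not on sample size, ICC or effect size. The standard-error figures do depend on the simulation assumptions, and the false significance on practice being the GEE cluster. The consequence is limited to this exploratory analysis, but the sentence should be corrected, because what it prints could be mistaken for treatment-effect heterogeneity.

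**What to change.** Delete the clinic-by-arm sentence and write: *Between-practice variation in outcomes will be reported descriptively within each arm; individual-clinic intervention effects are not estimable in this design.* This costs one SAP sentence and gives up only a result the design could not supply.

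If a test of heterogeneity is wanted, keep practice as the random effect or GEE cluster and choose one of these:

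- **(a) Arm-specific practice-by-time variance in the mixed models.** This is arguably closest to the plan's question. It needs a practice-by-time random term, which the models lack; it assumes equal practice variance across arms otherwise; and it does not cover BP control, which is analysed by GEE. For 80% power the variance of practice mean changes in one arm must be F(0.975; 14, 14) × F(0.80; 14, 14) = 2.98 × 1.58 = 4.7 times the other's. That ratio includes sampling error. Taking ICC 0.05 and 50 patients per practice as an illustrative split, the practice component itself must differ by (4.7 × 0.069 − 0.019) / 0.05 = 6.1-fold (8.3 at ICC 0.02, 5.4 at 0.10).
- **(b) Arm (or arm-by-time) by a practice characteristic such as FQHC status.** Section 4D lists 11 practices in the single non-FQHC system, so this cannot be separated from a system effect. With an assumed split of 6 and 5 non-FQHC and 9 and 10 FQHC practices by arm, the SE relative to the main effect is √[(1/6 + 1/5 + 1/9 + 1/10) / (2/15)] = 2.08. It is 2.02 if both later replacement practices joined that system, which the documents do not state. Applied to 11–13 points, the detectable interaction is roughly 22–27 points; treat this as illustrative.
- **(c) Arm by health system.** This is estimable where both arms occur. Section 4F allows as few as one practice per arm, so restrict it to systems with at least two in each arm (a judgement, not a rule in the documents). No power figure was computed; with so few practices per cell, expect low power.
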